### **16.2.2 Protocol deviation**

- 16.2.2.1 Listing of assessed protocol deviations
- 16.2.2.2 Listing of protocol deviations - monitoring plan (Appendix C)

### **16.2.3 Patients excluded from efficacy**

- 16.2.3.1 Listing of assignment of patients to analysis sets

### **16.2.4 Demographic data**

- 16.2.4.1 Listing of demographics

### **16.2.5 Compliance\_Drug concentration data**

- 16.2.5.1 Listing of compliance

### **16.2.6 Individual efficacy response data**

- 16.2.6.1 Listing of labile plasma iron (LPI)
- 16.2.6.2 Listing of serum ferritin (SF)
- 16.2.6.3 Listing of transferrin saturation (TSAT)

### **16.2.7 Adverse events**

- 16.2.7.1 Listing of medical events
- 16.2.7.2 Listing of adverse events
- 16.2.7.3 Listing of serious adverse events

### **16.2.8 Individual lab measurements by patient**

- 16.2.8.1 Listing of hematology
- 16.2.8.1a Listing of patients who have had abnormal values in hematology
- 16.2.8.1b Listing of patients who have had clinically significant values in hematology
- 16.2.8.2 Listing of urinalysis
- 16.2.8.3 Listing of serology
- 16.2.8.4 Listing of biochemistry
- 16.2.8.4a Listing of patients who have had abnormal values in biochemistry

16.2.8.4b Listing of patients who have had clinically significant values in biochemistry

16.2.8.5 Listing of prolactin

**16.2.9 Other measurements**

16.2.9.1 Listing of informed consent / Assent form

16.2.9.2 Listing of primary diagnosis

16.2.9.3 Listing of medical history

16.2.9.4 Listing of randomization

16.2.9.5 Listing of vital signs

16.2.9.6 Listing of physical examination

16.2.9.7 Listing of transfusion

16.2.9.8 Listing of exposure

16.2.9.9 Listing of concomitant medications

**TABLE SHELLS**

The following table shells provide a framework for the display of data from this study. These tables may not be designed exactly as shown in the shells, but are intended to reflect the general layout of the data that will be included in the clinical study report.

Note that 'c' in the table shells indicates an alphanumeric character and 'x' indicates a number from 0 to 9.

## 14.1 Patient disposition, demographics, and baseline data

Table 14.1.1 Patient disposition

	Deferiprone	Placebo	P-value (Fisher's exact test)
Randomized	xxx	xxx	
Exposed	xxx (xx%)	xxx (xx%)	0.xxxx
Completed	xxx (xx%)	xxx (xx%)	0.xxxx
Withdrawn	xxx (xx%)	xxx (xx%)	0.xxxx

Data source: 16.2.1.1 Listing of disposition

Table 14.1.2 Number of patients by study site

Country	Site	Deferiprone	Placebo	Total
Egypt	003	xx	xx	xx
	004	xx	xx	xx
	005	xx	xx	xx
Indonesia	006	xx	xx	xx
	Total	xx	xx	xx

Data source: 16.2.4.1 Listing of demographics

Table 14.1.3 Number of patients in safety, ITT, and PP populations

		Deferiprone	Placebo
Safety population		xx	xx
ITT population	Serum ferritin	xx	xx
	LPI	xx	xx
	TSAT	xx	xx
PP population	Serum ferritin	xx	xx
	LPI	xx	xx
	TSAT	xx	xx

Data source: 16.2.3.1 Listing of assignment of patients to analysis sets

Table 14.1.4 Reasons for not completing the study

		Deferiprone	Placebo	Total
		n (%)	n (%)	n (%)
N		xx (100)	xx (100)	xx (100)
Reason:	Detail			
Adverse event	Ccccc	xx (xx)	xx (xx)	xx (xx)
	Ccccc	xx (xx)	xx (xx)	xx (xx)
Withdrawal by parent/guardian	Ccccc	xx (xx)	xx (xx)	xx (xx)
	Ccccc	xx (xx)	xx (xx)	xx (xx)
Lost to follow-up	Ccccc	xx (xx)	xx (xx)	xx (xx)
	Ccccc	xx (xx)	xx (xx)	xx (xx)
Physician decision	Ccccc	xx (xx)	xx (xx)	xx (xx)
	Ccccc	xx (xx)	xx (xx)	xx (xx)
Protocol deviation	Ccccc	xx (xx)	xx (xx)	xx (xx)
	Ccccc	xx (xx)	xx (xx)	xx (xx)
Lack of efficacy	Ccccc	xx (xx)	xx (xx)	xx (xx)
	Ccccc	xx (xx)	xx (xx)	xx (xx)
Other	Ccccc	xx (xx)	xx (xx)	xx (xx)
	Ccccc	xx (xx)	xx (xx)	xx (xx)
Total		xx (xx)	xx (xx)	xx (xx)

Data source: 16.2.1.1 Listing of disposition

Table 14.1.5 Demographics data

	Deferiprone	Placebo	Total	
N	xx	xx	xx	p-value §
Age (years):				0xxxx
Mean	xx.x	xx.x	xx.x	
SD	xx.x	xx.x	xx.x	
Minimum	xx.x	xx.x	xx.x	
Maximum	xx.x	xx.x	xx.x	
Sex: n (%)				0xxxx
Female	xx (xx)	xx (xx)	xx (xx)	
Male	xx (xx)	xx (xx)	xx (xx)	
Ethnic Origin: n (%)				0xxxx
Hispanic/Latino	xx (xx)	xx (xx)	xx (xx)	
Not Hispanic/Latino	xx (xx)	xx (xx)	xx (xx)	
Racial Origin: n (%)				0xxxx
Asian	xx (xx)	xx (xx)	xx (xx)	
American Indian or Alaska Native	xx (xx)	xx (xx)	xx (xx)	
Black or African American	xx (xx)	xx (xx)	xx (xx)	
Native Hawaiian or Other Pacific Islander	xx (xx)	xx (xx)	xx (xx)	
White	xx (xx)	xx (xx)	xx (xx)	
Other	xx(xx)	xx(xx)	xx(xx)	

§T-test for age; Fisher's exact test for sex, ethnic origin, and racial origin

Data source: 16.2.4.1 Listing of demographics

Table 14.1.6 Medical history

	Deferiprone		Placebo		Total	
N	xx		xx		xx	
Illness/Event by MedDRA Primary System Organ Class and Preferred Term	Resolved n (%)	ongoing n (%)	resolved n (%)	ongoing n (%)	resolved n (%)	ongoing n (%)
Ccccc	xx (xx)	xx (xx)	xx (xx)	xx (xx)	xx (xx)	xx (xx)
Ccccc	xx (xx)	xx (xx)	xx (xx)	xx (xx)	xx (xx)	xx (xx)
Ccccc	xx (xx)	xx (xx)	xx (xx)	xx (xx)	xx (xx)	xx (xx)
Ccccc	xx (xx)	xx (xx)	xx (xx)	xx (xx)	xx (xx)	xx (xx)

Data source: 16.2.9.3 Listing of medical history

Table 14.1.7 Serum ferritin, LPI, and TSAT at baseline

	Deferiprone	Placebo	
N	xx	xx	
	Mean ± SD (Min, Max)	Mean ± SD (Min, Max)	P-value (t-test)
Serum Ferritin ( $\mu$ g/L)	xxxx ± xxxx (xxxx, xxxx)	xxxx ± xxxx (xxxx, xxxx)	0.xxxx
LPI ( $\mu$ M)	x.xx ± x.xx (x.xx, x.xx)	x.xx ± x.xx (x.xx, x.xx)	0.xxxx
TSAT (%)	xx ± xx (xx, xx)	xx ± xx (xx, xx)	0.xxxx

Data source: 16.2.6.2 Listing of serum ferritin (SF)

16.2.6.1 Listing of labile plasma iron (LPI)

16.2.6.3 Listing of transferrin saturation (TSAT)

Table 14.1.8 Serology data at baseline

Positive result	Deferiprone	Placebo	P-value (Fisher's exact test)
Hepatitis B	xx% (xx / xx)	xx% (xx / xx)	0.xxxx
Hepatitis C	xx% (xx / xx)	xx% (xx / xx)	0.xxxx
HIV	xx% (xx / xx)	xx% (xx / xx)	0.xxxx

Data source: 16.2.8.3 Listing of serology

## 14.2 Efficacy Analyses

### 14.2.1 Serum Ferritin (μg/L)

Table 14.2.1.1 Serum ferritin (μg/L) at each assessment – ITT population

	Deferiprone		Placebo		
	N	Mean ± SD (Min, Max)	N	Mean ± SD (Min, Max)	P-value (t-test)
Baseline	xx	xxxx ± xxxx (xxxx,xxxx)	xx	xxxx ± xxxx (xxxx,xxxx)	0.xxxx
Month 1	xx	xxxx ± xxxx (xxxx,xxxx)	xx	xxxx ± xxxx (xxxx,xxxx)	0.xxxx
Month 2	xx	xxxx ± xxxx (xxxx,xxxx)	xx	xxxx ± xxxx (xxxx,xxxx)	0.xxxx
Month 3	xx	xxxx ± xxxx (xxxx,xxxx)	xx	xxxx ± xxxx (xxxx,xxxx)	0.xxxx
Month 4	xx	xxxx ± xxxx (xxxx,xxxx)	xx	xxxx ± xxxx (xxxx,xxxx)	0.xxxx
Month 5	xx	xxxx ± xxxx (xxxx,xxxx)	xx	xxxx ± xxxx (xxxx,xxxx)	0.xxxx
Month 6	xx	xxxx ± xxxx (xxxx,xxxx)	xx	xxxx ± xxxx (xxxx,xxxx)	0.xxxx
Month 7	xx	xxxx ± xxxx (xxxx,xxxx)	xx	xxxx ± xxxx (xxxx,xxxx)	0.xxxx
Month 8	xx	xxxx ± xxxx (xxxx,xxxx)	xx	xxxx ± xxxx (xxxx,xxxx)	0.xxxx
Month 9	xx	xxxx ± xxxx (xxxx,xxxx)	xx	xxxx ± xxxx (xxxx,xxxx)	0.xxxx
Month 10	xx	xxxx ± xxxx (xxxx,xxxx)	xx	xxxx ± xxxx (xxxx,xxxx)	0.xxxx
Month 11	xx	xxxx ± xxxx (xxxx,xxxx)	xx	xxxx ± xxxx (xxxx,xxxx)	0.xxxx
Month 12	xx	xxxx ± xxxx (xxxx,xxxx)	xx	xxxx ± xxxx (xxxx,xxxx)	0.xxxx

Data source: 16.2.6.2 Listing of serum ferritin (SF)

Note: Similar Table 14.2.1.1a will be made for PP population

Table 14.2.1.2 Change in serum ferritin ( $\mu\text{g/L}$ ) from baseline to each follow-up assessment – ITT population

	Deferiprone		Placebo		
	N	Mean $\pm$ SD (Min, Max)	N	Mean $\pm$ SD (Min, Max)	P-value (t-test)
Month 1	xx	xxxx $\pm$ xxxx (xxxx,xxxx)	xx	xxxx $\pm$ xxxx (xxxx,xxxx)	0.xxxx
Month 2	xx	xxxx $\pm$ xxxx (xxxx,xxxx)	xx	xxxx $\pm$ xxxx (xxxx,xxxx)	0.xxxx
Month 3	xx	xxxx $\pm$ xxxx (xxxx,xxxx)	xx	xxxx $\pm$ xxxx (xxxx,xxxx)	0.xxxx
Month 4	xx	xxxx $\pm$ xxxx (xxxx,xxxx)	xx	xxxx $\pm$ xxxx (xxxx,xxxx)	0.xxxx
Month 5	xx	xxxx $\pm$ xxxx (xxxx,xxxx)	xx	xxxx $\pm$ xxxx (xxxx,xxxx)	0.xxxx
Month 6	xx	xxxx $\pm$ xxxx (xxxx,xxxx)	xx	xxxx $\pm$ xxxx (xxxx,xxxx)	0.xxxx
Month 7	xx	xxxx $\pm$ xxxx (xxxx,xxxx)	xx	xxxx $\pm$ xxxx (xxxx,xxxx)	0.xxxx
Month 8	xx	xxxx $\pm$ xxxx (xxxx,xxxx)	xx	xxxx $\pm$ xxxx (xxxx,xxxx)	0.xxxx
Month 9	xx	xxxx $\pm$ xxxx (xxxx,xxxx)	xx	xxxx $\pm$ xxxx (xxxx,xxxx)	0.xxxx
Month 10	xx	xxxx $\pm$ xxxx (xxxx,xxxx)	xx	xxxx $\pm$ xxxx (xxxx,xxxx)	0.xxxx
Month 11	xx	xxxx $\pm$ xxxx (xxxx,xxxx)	xx	xxxx $\pm$ xxxx (xxxx,xxxx)	0.xxxx
Month 12	xx	xxxx $\pm$ xxxx (xxxx,xxxx)	xx	xxxx $\pm$ xxxx (xxxx,xxxx)	0.xxxx

Data source: 16.2.6.2 Listing of serum ferritin (SF)

Note: Similar Table 14.2.1.2a will be made for PP population

Table 14.2.1.3 LS Means for change in serum ferritin ( $\mu\text{g/L}$ ) from ANCOVA model at each follow-up assessment – ITT population

	Deferiprone	Placebo	Deferiprone Minus Placebo	95% C.I.
N	xx	xx	xx	
	LS Mean $\pm$ SE	LS Mean $\pm$ SE	LS Mean $\pm$ SE	
Month 1	xxxx $\pm$ xxxx	xxxx $\pm$ xxxx	xxxx $\pm$ xxxx	(xxxx, xxxx)
Month 2	xxxx $\pm$ xxxx	xxxx $\pm$ xxxx	xxxx $\pm$ xxxx	(xxxx, xxxx)
Month 3	xxxx $\pm$ xxxx	xxxx $\pm$ xxxx	xxxx $\pm$ xxxx	(xxxx, xxxx)
Month 4	xxxx $\pm$ xxxx	xxxx $\pm$ xxxx	xxxx $\pm$ xxxx	(xxxx, xxxx)
Month 5	xxxx $\pm$ xxxx	xxxx $\pm$ xxxx	xxxx $\pm$ xxxx	(xxxx, xxxx)
Month 6	xxxx $\pm$ xxxx	xxxx $\pm$ xxxx	xxxx $\pm$ xxxx	(xxxx, xxxx)
Month 7	xxxx $\pm$ xxxx	xxxx $\pm$ xxxx	xxxx $\pm$ xxxx	(xxxx, xxxx)
Month 8	xxxx $\pm$ xxxx	xxxx $\pm$ xxxx	xxxx $\pm$ xxxx	(xxxx, xxxx)
Month 9	xxxx $\pm$ xxxx	xxxx $\pm$ xxxx	xxxx $\pm$ xxxx	(xxxx, xxxx)
Month 10	xxxx $\pm$ xxxx	xxxx $\pm$ xxxx	xxxx $\pm$ xxxx	(xxxx, xxxx)
Month 11	xxxx $\pm$ xxxx	xxxx $\pm$ xxxx	xxxx $\pm$ xxxx	(xxxx, xxxx)
Month 12	xxxx $\pm$ xxxx	xxxx $\pm$ xxxx	xxxx $\pm$ xxxx	(xxxx, xxxx)

Data source: 16.2.6.2 Listing of serum ferritin (SF)

Note: Similar Table 14.2.1.3a will be made for PP population

Table 14.2.1.4 Trend analysis for serum ferritin ( $\mu\text{g/L}$ ) over time – ITT population

Rate of change per month	Deferiprone	Placebo	Deferiprone minus Placebo	P-value
Mean $\pm$ SE	xxxx $\pm$ xxxx	xxxx $\pm$ xxxx	xxxx $\pm$ xxxx	0.xxxx

Data source: 16.2.6.2 Listing of serum ferritin (SF)

Note: Similar Table 14.2.1.4a will be made for PP population

Table 14.2.1.5 Percent of patients who had serum ferritin  $< 1000 \mu\text{g/L}$  at each assessment – ITT population

	Deferiprone	Placebo	P-value (Fisher's exact test)
Baseline	xx% (xx / xx)	xx% (xx / xx)	0.xxxx
Month 1	xx% (xx / xx)	xx% (xx / xx)	0.xxxx
Month 2	xx% (xx / xx)	xx% (xx / xx)	0.xxxx
Month 3	xx% (xx / xx)	xx% (xx / xx)	0.xxxx
Month 4	xx% (xx / xx)	xx% (xx / xx)	0.xxxx
Month 5	xx% (xx / xx)	xx% (xx / xx)	0.xxxx
Month 6	xx% (xx / xx)	xx% (xx / xx)	0.xxxx
Month 7	xx% (xx / xx)	xx% (xx / xx)	0.xxxx
Month 8	xx% (xx / xx)	xx% (xx / xx)	0.xxxx
Month 9	xx% (xx / xx)	xx% (xx / xx)	0.xxxx
Month 10	xx% (xx / xx)	xx% (xx / xx)	0.xxxx
Month 11	xx% (xx / xx)	xx% (xx / xx)	0.xxxx
Month 12	xx% (xx / xx)	xx% (xx / xx)	0.xxxx

Data source: 16.2.6.2 Listing of serum ferritin (SF)

Note: Similar Table 14.2.1.5a will be made for PP population

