Patients will remain in the study for 12 months or until their SF level is found to be  $\geq 1000 \mu\text{g/L}$  at 2 consecutive visits, whichever comes first. Since SF level may be impacted by the presence of infection, it must additionally be verified that the child has had no signs of infection in the previous 7 days, including the day of the visit, and that the level of C-reactive protein (CRP) is no greater than 20% higher than the normal range for the patient's age. If there are signs of infection and/or the CRP level is above this threshold, the SF level must be checked again a minimum of one week later. (Note: If an investigator has valid reason to believe that an SF level  $\geq 1000 \mu\text{g/L}$  may be attributable to infection even if this is not indicated by the CRP result, SF may be rechecked once more a minimum of one week later.)

Patients whose SF levels are still under  $1000 \mu\text{g/L}$  at 12 months will be offered participation in an extension study, LA55-EXT, in which they will continue to receive their assigned study product for up to 2 more years. Those who are terminated early will not be eligible to enroll in the extension study.

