### 9.2 Determination of Sample Size and Study Power

The sample size for this study is 64 patients, randomized in a 1:1 ratio to the two arms. With this number of patients, there will be over 90% power to detect a statistically significant difference ( $\alpha = 0.05$ ) between the two treatment groups in the percentage of patients who have a serum ferritin level  $< 1000 \mu\text{g/L}$  at Month 12 if the deferiprone arm and the placebo arm have an expected incidence of 70% and 20%, respectively.

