### 3.2 Number of Patients

A planned total of 64 patients are to be enrolled in the study, 32 in each arm.

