## **5. Statistical Analysis**

A two-sided p-value of 0.05 will be used as the significance level for the determination of statistical significance in all statistical tests.

All statistical analyses of efficacy and safety data will be performed using SAS (version 9.4 or higher) on the Windows operating system.

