### **5.1 Study Populations**

#### **5.1.1 Intent-to-Treat Population**

The intent-to-treat (ITT) population will be composed of patients who were randomized, have received at least one dose of study medication, and have had at least one post-baseline measurement on the efficacy variables. All efficacy endpoints will be analyzed for the ITT population, which represents the primary analysis population.

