## 5.6 Analysis of Efficacy

The percentage of patients who have not reached levels of  $LPI \geq 0.6 \mu M$ ,  $TSAT \geq 60\%$ , or  $SF \geq 1000 \mu g/L$  will be compared between the two treatment groups at each monthly time point as well as at the end of study, using the Fisher's exact test. (Note: the repeated SF value will be used to determine this for those patients whose SF is  $\geq 1000 \mu g/L$ .)

The effect of baseline value on each of the 3 efficacy endpoints will be examined in a covariate analysis. As an example for serum ferritin, the following SAS code of MIXED procedure will be used to produce the differences in Least Squares (LS) Mean of change in serum ferritin at Months 1, 2, 3, 4, 5, 6, 7, 8, 9, 10, 11, and 12 between deferiprone and placebo groups and the corresponding 95% confidence intervals.

```

proc mixed data=sf;
  class patient base_sf treat month;
  model sf_change = base_sf treat month treat*month /
    noint solution ddfm=kr;
  repeated month / Patient=patient(treat) type=ar(1);
  lsmeans treat*month;
  estimate 'Deferiprone - Placebo at Month 1'
    treat 1 -1
    treat*month  1 0 0 0 0 0 0 0 0 0 0 0
                 -1 0 0 0 0 0 0 0 0 0 0 0 / cl alpha=0.05;
  estimate 'Deferiprone - Placebo at Month 2'
    treat 1 -1
    treat*month  0 1 0 0 0 0 0 0 0 0 0 0
                 0 -1 0 0 0 0 0 0 0 0 0 0 / cl alpha=0.05;
  estimate 'Deferiprone - Placebo at Month 3'
    treat 1 -1
    treat*month  0 0 1 0 0 0 0 0 0 0 0 0
                 0 0 -1 0 0 0 0 0 0 0 0 0 / cl alpha=0.05;
  estimate 'Deferiprone - Placebo at Month 4'
    treat 1 -1
    treat*month  0 0 0 1 0 0 0 0 0 0 0 0
                 0 0 0 -1 0 0 0 0 0 0 0 0 / cl alpha=0.05;
  estimate 'Deferiprone - Placebo at Month 5'
    treat 1 -1
    treat*month  0 0 0 0 1 0 0 0 0 0 0 0
                 0 0 0 0 -1 0 0 0 0 0 0 0 / cl alpha=0.05;
  estimate 'Deferiprone - Placebo at Month 6'
    treat 1 -1
    treat*month  0 0 0 0 0 1 0 0 0 0 0 0
                 0 0 0 0 0 -1 0 0 0 0 0 0 / cl alpha=0.05;

```

```

estimate 'Deferiprone - Placebo at Month 7'
  treat 1 -1
  treat*month  0 0 0 0 0 0  1 0 0 0 0 0
                0 0 0 0 0 0 -1 0 0 0 0 0/ cl alpha=0.05;
estimate 'Deferiprone - Placebo at Month 8'
  treat 1 -1
  treat*month  0 0 0 0 0 0  1 0 0 0 0
                0 0 0 0 0 0 0 -1 0 0 0 0/ cl alpha=0.05;
estimate 'Deferiprone - Placebo at Month 9'
  treat 1 -1
  treat*month  0 0 0 0 0 0 0 0  1 0 0 0
                0 0 0 0 0 0 0 0 -1 0 0 0/ cl alpha=0.05;

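### The monthly t-tests on mean serum ferritin are labelled ITT but use only children not yet withdrawn for confirmed ferritin of 1000 µg/L or more, which biases the late visits toward no difference

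*SAP*

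**What the plan says.** **The tests.** In the SAP table shells, section 14.2.1, Table 14.2.1.1 gives mean SF at each visit and Table 14.2.1.2 gives mean change "from baseline to each follow-up assessment – ITT population". Both run monthly to Month 12, print a separate N per arm and visit, and end in a t-test p-value column. Per-protocol copies are planned. SAP section 5 says "A two-sided p-value of 0.05 will be used as the significance level" for all tests, so these p-values are inferential as written.

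**The population.** Besides randomisation and one dose, SAP 5.1.1 requires only that children "have had at least one post-baseline measurement on the efficacy variables". A value at the visit being tested is not needed, and no missing-data rule covers these tables.

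**The removal rule.** Protocol 3.1: "Patients will remain in the study for 12 months or until their SF level is found to be" 1000 µg/L or more at two consecutive visits. Protocol 4.5 makes this withdrawal mandatory once infection and raised CRP are excluded. Protocol 5.1 applies it as soon as the second result is known, and 4.5.1 rules out replacement. The early termination visit for these children lists haematology and chemistry but no SF.

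**The methods text.** SAP 5.6 does not mention the t-tests. It specifies a repeated-measures model that "will be used to produce the differences in Least Squares (LS) Mean of change in serum ferritin" by month. Table 14.2.1.3 reports that model with confidence intervals but no p-value.

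**The concern.** The ITT label implies a comparison of SF in the groups as randomised. What the t-test compares at Month 12 is mean SF among children not yet removed for high SF. The sample is truncated on the variable under test, and the planning figures imply that this happens much more often on placebo. The better the drug works, the more high-ferritin placebo children are missing from the late rows and the smaller the tabled difference becomes. Mean-line Figures 14.2.1 and 14.2.4, if drawn from the same observed values, would show placebo flattening for the same reason. Because Table 14.2.1.3 carries no p-value, the only visit-by-visit p-values on mean SF would come from the biased comparison.

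**Working it through.** **1. The plan's own power figure.** Protocol 9.2 states "there will be over 90% power to detect a statistically significant difference" with an "expected incidence of 70% and 20%, respectively". SAP 3.2: "A planned total of 64 patients are to be enrolled in the study, 32 in each arm". With p̄ = 0.45 and n = 32:

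- null SE = √(2 × 0.45 × 0.55 / 32) = 0.1244
- alternative SE = √((0.7 × 0.3 + 0.2 × 0.8) / 32) = 0.1075
- power = Φ((0.50 − 1.96 × 0.1244) / 0.1075) = Φ(2.38) = 99.1%

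Exact enumeration of Fisher's test gives 98.3%. The stated figure is reproduced, and the primary test does not use the mean-SF t-tests.

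**2. Model for mean SF.** The documents give no SF slope, SD or trajectory, so the following are assumptions.

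- SF at month t = b + s·t + e, with b uniform on 200–600 µg/L (the entry range).
- s is normal, with SD 15–60 µg/L per month; e has SD 50–150.
- Arm mean slopes are set so that 70% and 20% have SF < 1000 at Month 12.
- A child leaves after two consecutive values ≥ 1000. Other withdrawals and recheck delays are ignored.

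Share kept = difference among children still observed ÷ difference had all 32 per arm been followed. In the case with slope SD 25 and visit SD 100, the mean slopes are 35.6 and 73.5. The full difference is about 12 × (73.5 − 35.6) = 455 (simulated 457), and the observed difference is 221, so 221 / 457 = 48% is kept.

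Month 12, linear rise:

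| Slope SD / visit SD | Full difference in SF | Observed | SF kept | Change kept | Children left, deferiprone v placebo | Power of SF t-test, observed |
|---|---|---|---|---|---|---|
| 15 / 150 | 360 | 223 | 62% | 75% | 27.1 v 12.0 | 80% |
| 25 / 100 | 457 | 221 | 48% | 56% | 26.2 v 10.8 | 63% |
| 40 / 100 | 680 | 291 | 43% | 47% | 25.0 v 9.3 | 50.5% |
| 60 / 50 | 985 | 379 | 38% | 40% | 24.1 v 8.3 | 41% |

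Power with full follow-up is about 100% throughout. Over the whole linear grid:

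- Month 12 loss is 38–62% for SF and 25–60% for change.
- SF kept is 75–99% at Month 6 and 49–82% at Month 9.

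For the t-test on change, further runs of this kind give a Month 12 difference 29–65% smaller and power of 48–93%. With exponential rise, only 17–48% of the difference in change is kept.

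**3. Plausibility of the upper end.** At slope SD 60 the calibrated deferiprone mean slope is 18.4, so Φ(−18.4 / 60) = 38% of treated children would have falling ferritin despite transfusion. About 20% would be below zero by Month 12. At slope SD 40 about 7% would be below zero.

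**4. Who remains.** In the linear grid, 21–57% of the placebo values still observed at Month 12 are ≥ 1000. They are first or isolated high values, or second ones drawn at that visit.

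**5. Whether the section 5.6 model can replace the t-tests.** As coded, base_sf is in the CLASS statement. With 64 distinct baselines, its 64 columns already separate the arms, so treat adds nothing. Month adds 11 and treat*month adds 11, giving rank 64 + 11 + 11 = 86. Adding the Month 12 treatment contrast raises the rank to 87, so it is not estimable.

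With baseline continuous, the share of the full-follow-up Month 12 difference recovered from the truncated data is:

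| Analysis | Linear | Exponential |
|---|---|---|
| t-test on remaining children | 43–57% | 27% |
| AR(1) | 66–76% | 42% |
| Unstructured covariance | 99–100% | 89% |

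**The case against.** No planned conclusion rests on these p-values. Mean SF and mean change are neither primary nor secondary endpoints (SAP 5.2), the t-tests are absent from SAP 5.6, and the shells are said to be adjustable. The bias runs toward no difference, so it cannot create a false efficacy claim. The per-visit N, the Kaplan-Meier curves and the table of reasons for not completing already show much of the attrition. Full follow-up without chelation is also a hypothetical benchmark, since Protocol 3.2 says children leave so that standard chelation is not delayed. All of this stands, and it limits the point to supportive tables.

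A reader might also infer three stronger things that the documents do not support:

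- *Only low-ferritin children remain.* Exit needs two consecutive high values, so a material share of the remaining placebo values at Month 12 are at or above 1000.
- *About half the effect is lost.* No document figure fixes the loss. It depends on assumed slope spread, noise and trajectory shape.
- *The late rows would contradict the primary result.* In the simulations the difference shrinks but keeps its direction.

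The objection does not remove the fault: a test labelled ITT, at a stated significance level, compares groups truncated on its own outcome.

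**Conclusion.** The point holds for the late visits of Tables 14.2.1.1 and 14.2.1.2 and their per-protocol versions. As laid out, these are observed-case comparisons biased toward no effect. Under linear rise calibrated to 70% v 20%, the Month 12 difference in change is roughly 25–65% smaller than under hypothetical full follow-up without chelation, and power falls from about 100% to roughly 50–90%. The upper end of the loss depends on implausibly large slope spread; exponential rise would make the loss larger. The loss at Month 6 is small. The direction follows from the documents, but the size rests on the assumptions listed in the working. The change should be made, but the primary Fisher analysis does not depend on it. Table 14.2.1.3 cannot simply take over, because its model as coded does not yield the treatment contrast when baselines are distinct.

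**What to change.** 1. Delete the post-baseline t-test p-values from Tables 14.2.1.1 and 14.2.1.2 and the per-protocol copies, and label the tables observed-case.
2. Add the cumulative number per arm withdrawn for SF ≥ 1000 µg/L at each visit, in these tables and under Figures 14.2.1 and 14.2.4.
3. Take the between-arm SF contrast from the section 5.6 repeated-measures model. First remove base_sf from CLASS so that it enters as a continuous covariate, and replace AR(1) with an unstructured or similarly flexible covariance. State the missing-at-random assumption: withdrawal for high SF depends on observed SF values.
4. Optionally, add a row for the last SF up to Month 12 in all ITT children, labelled as mixing follow-up times and conservative.

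The cost is an edit to the shells and to a few lines of SAS code, with no new data. An unstructured 12-visit covariance may not converge with 64 children, so the SAP should name a fallback structure in advance.
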